## **10. Future Biomedical Research Study Population**

Every effort will be made to recruit all participants diagnosed and treated on Sponsor clinical trials for Future Biomedical Research.

## **11. Risks Versus Benefits of Future Biomedical Research**

For future biomedical research, risks to the participant have been minimized. No additional risks to the participant have been identified as no additional specimens are being collected for Future Biomedical Research (i.e., only leftover samples are being retained).'

The Sponsor has developed strict security, policies and procedures to address participant data privacy concerns. Data privacy risks are largely limited to rare situations involving possible breach of confidentiality. In this highly unlikely situation there is risk that the information, like all medical information, may be misused.

## **12. Questions**

Any questions related to the future biomedical research should be e-mailed directly to [[contact]](mailto:[contact]).

## 12.7 Appendix 7: Description of the iRECIST Process for Assessment of Disease Progression

### Assessment at Screening and Prior to RECIST 1.1 Progression

Until radiographic disease progression based on RECIST 1.1, there is no distinct iRECIST assessment.

### Assessment and Decision at RECIST 1.1 Progression

For participants who show evidence of radiological PD by RECIST 1.1 as determined by the Investigator, the Investigator will decide whether to continue a participant on study treatment until repeat imaging is obtained (using iRECIST for participant management (see Table [X])). This decision by the Investigator should be based on the participant's overall clinical condition.

Clinical stability is defined as the following:

- Absence of symptoms and signs indicating clinically significant progression of disease
- No decline in ECOG performance status
- No requirements for intensified management, including increased analgesia, radiation, or other palliative care

Any participant deemed clinically unstable should be discontinued from study treatment at site-assessed first radiologic evidence of PD and is not required to have repeat tumor imaging for confirmation of PD by iRECIST.

If the Investigator decides to continue treatment, the participant may continue to receive study treatment and the tumor assessment should be repeated 4 to 8 weeks later to confirm PD by iRECIST, per Investigator assessment. Images should continue to be sent in to the central imaging vendor for potential retrospective BICR.

Tumor flare may manifest as any factor causing radiographic progression per RECIST 1.1, including:

- Increase in the sum of diameters of target lesion(s) identified at baseline to  $\geq 20\%$  and  $\geq 5$  mm from nadir
  - Note: the iRECIST publication uses the terminology “sum of measurements”, but “sum of diameters” will be used in this protocol, consistent with the original RECIST 1.1 terminology.
- Unequivocal progression of non-target lesion(s) identified at baseline
- Development of new lesion(s)

iRECIST defines new response categories, including iUPD (unconfirmed progressive disease) and iCPD (confirmed progressive disease). For purposes of iRECIST assessment, the first visit showing progression according to RECIST 1.1 will be assigned a visit (overall) response of iUPD, regardless of which factors caused the progression.

At this visit, target and non-target lesions identified at baseline by RECIST 1.1 will be assessed as usual.

New lesions will be classified as measurable or non-measurable, using the same size thresholds and rules as for baseline lesion assessment in RECIST 1.1. From measurable new lesions, up to 5 lesions total (up to 2 per organ), may be selected as New Lesions – Target. The sum of diameters of these lesions will be calculated and kept distinct from the sum of diameters for target lesions at baseline. All other new lesions will be followed qualitatively as New Lesions – Non-target.

#### Assessment at the Confirmatory Imaging

On the confirmatory imaging, the participant will be classified as progression confirmed (with an overall response of iCPD), or as showing persistent unconfirmed progression (with an overall response of iUPD), or as showing disease stability or response (iSD/iPR/iCR).

#### Confirmation of Progression

Progression is considered confirmed, and the overall response will be iCPD, if ANY of the following occurs:

- Any of the factors that were the basis for the initial iUPD show worsening
  - For target lesions, worsening is a further increase in the sum of diameters of  $\geq 5$  mm, compared to any prior iUPD time point
  - For non-target lesions, worsening is any significant growth in lesions overall, compared to a prior iUPD time point; this does not have to meet the “unequivocal” standard of RECIST 1.1
  - For new lesions, worsening is any of these:
    - An increase in the new lesion sum of diameters by  $\geq 5$  mm from a prior iUPD time point
    - Visible growth of new non-target lesions
    - The appearance of additional new lesions
- Any new factor appears that would have triggered PD by RECIST 1.1

#### Persistent iUPD

Progression is considered not confirmed, and the overall response remains iUPD, if:

- None of the progression-confirming factors identified above occurs AND
- The target lesion sum of diameters (initial target lesions) remains above the initial PD threshold (by RECIST 1.1)

Additional imaging for confirmation should be scheduled 4 to 8 weeks from the imaging on which iUPD is seen. This may correspond to the next visit in the original visit schedule. The assessment of the subsequent confirmation imaging proceeds in an identical manner, with possible outcomes of iCPD, iUPD, and iSD/iPR/iCR.

### Resolution of iUPD

Progression is considered not confirmed, and the overall response becomes iSD/iPR/iCR, if:

- None of the progression-confirming factors identified above occurs, AND
- The target lesion sum of diameters (initial target lesions) is not above the initial PD threshold.

The response is classified as iSD or iPR (depending on the sum of diameters of the target lesions), or iCR if all lesions resolve.

In this case, the initial iUPD is considered to be pseudo-progression, and the level of suspicion for progression is “reset”. This means that the next visit that shows radiographic progression, whenever it occurs, is again classified as iUPD by iRECIST, and the confirmation process is repeated before a response of iCPD can be assigned.

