### Detection of Progression at Visits After Pseudo-Progression Resolves

After resolution of pseudo-progression (ie, achievement of iSD/iPR/iCR), iUPD is indicated by any of the following events:

- Target lesions
  - Sum of diameters reaches the PD threshold ( $\geq 20\%$  and  $\geq 5$  mm increase from nadir) either for the first time, or after resolution of previous pseudo-progression. The nadir is always the smallest sum of diameters seen during the entire trial, either before or after an instance of pseudo-progression.
- Non-target lesions
  - If non-target lesions have never shown unequivocal progression, their doing so for the first time results in iUPD.
  - If non-target lesions have shown previous unequivocal progression, and this progression has not resolved, iUPD results from any significant further growth of non-target lesions, taken as a whole.

- New lesions
  - New lesions appear for the first time
  - Additional new lesions appear
  - Previously identified new target lesions show an increase of  $\geq 5$  mm in the new lesion sum of diameters, from the nadir value of that sum
  - Previously identified non-target lesions show any significant growth

If any of the events above occur, the overall response for that visit is iUPD, and the iUPD evaluation process (see Assessment at the Confirmatory Imaging above) is repeated. Progression must be confirmed before iCPD can occur.

The decision process is identical to the iUPD confirmation process for the initial PD, with one exception: if new lesions occurred at a prior instance of iUPD, and at the confirmatory imaging the burden of new lesions has increased from its smallest value (for new target lesions, the sum of diameters is  $\geq 5$  mm increased from its nadir), then iUPD cannot resolve to iSD or iPR. It will remain iUPD until either a decrease in the new lesion burden allows resolution to iSD or iPR, or until a confirmatory factor causes iCPD.

Additional details about iRECIST are provided in the iRECIST publication [Seymour, L., et al 2017].

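### In Appendix 7, a first iUPD triggered only by new or non-target lesions cannot persist, so an iPR can count in the iRECIST ORR while those lesions are still present

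*Combined protocol and SAP*

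**What the plan says.** All of the rules are in Appendix 7 (Section 12.7).

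- **Trigger.** Under Assessment and Decision at RECIST 1.1 Progression, "the first visit showing progression according to RECIST 1.1 will be assigned a visit (overall) response of iUPD, regardless of which factors caused the progression". The listed factors are target-sum growth, unequivocal non-target progression and new lesions.
- **Confirmation (iCPD).** This needs worsening of a factor that caused the iUPD, or a fresh one: "Any new factor appears that would have triggered PD by RECIST 1.1". Lesions that are merely unchanged do not confirm. For example, "For non-target lesions, worsening is any significant growth in lesions overall, compared to a prior iUPD time point".
- **Persistent iUPD.** No confirming factor occurs, and "The target lesion sum of diameters (initial target lesions) remains above the initial PD threshold (by RECIST 1.1").
- **Resolution of iUPD.** No confirming factor occurs, and "The target lesion sum of diameters (initial target lesions) is not above the initial PD threshold". The category is then iSD or iPR according to the target sum. Only iCR requires every lesion to have gone. The episode is labelled pseudo-progression and suspicion is reset.
- **Later episodes.** After an earlier reset the process is the same with one exception. If new lesions belonged to an earlier iUPD and their burden at the confirmatory scan is above its smallest value, the response stays iUPD "until either a decrease in the new lesion burden allows resolution to iSD or iPR" or a confirming factor gives iCPD.

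Sections 4 and 10.4.1 make investigator-assessed ORR by RECIST 1.1 and by iRECIST a secondary endpoint. Section 10.6.1 gives a Clopper-Pearson interval for ORR and no rule for iRECIST best overall response. Section 9.2.3 asks for response to be confirmed by imaging at least 4 weeks later.

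**The concern.** Three kinds of finding can open an iUPD, but only one of them, the initial target-lesion sum, decides whether an unconfirmed iUPD stays open. When new or non-target lesions opened the episode, the closing test does not look at what caused it. A participant can therefore have the progression-defining lesions still visible, be reset, and be carried as iPR.

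Nothing downstream removes that iPR from the numerator. The confirmation rule in Section 9.2.3 does not mention remaining progression lesions, and Section 10 does not define an iRECIST responder. Section 5.1.1 allows preliminary clinical benefit data to inform the choice of the preliminary RP2D, and Section 10.7 has efficacy examined continuously, so the iRECIST ORR may be read while dose decisions are being made. Exploratory iRECIST PFS could also be lengthened, because after a reset the next progression is again unconfirmed and must be confirmed afresh. The PFS methods are left to the sSAP, so this effect is only possible.

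**Working it through.** The plan states no figure for this point. The check is of the classification rule, followed by simple arithmetic for its size.

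**Step 1: outcomes of a first episode when nothing worsens at the confirmatory scan** (Confirmation of Progression, Persistent iUPD, Resolution of iUPD)

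| What triggered the iUPD | Target sum above PD threshold | Target sum not above |
|---|---|---|
| New lesions only | iCPD (a new PD factor) | iSD/iPR |
| Non-target only | iCPD (a new PD factor) | iSD/iPR |
| New and non-target | iCPD (a new PD factor) | iSD/iPR |
| Target sum, alone or with others | iUPD | iSD/iPR |

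In the first three rows persistent iUPD cannot be reached. In the last row a mixed trigger also resolves once the target sum falls back, even if the new or non-target lesions remain.

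**Step 2: worked case** (illustrative sizes)

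- Baseline target sum is 100 mm. At week 9 the sum is 65 mm and there is a new 20 mm lesion. This is RECIST 1.1 PD, hence iUPD.
- The PD threshold from a nadir of 65 mm, using the 20% and 5 mm rule in Appendix 7, is max(65 × 1.20, 65 + 5) = max(78, 70) = 78 mm.
- At the confirmatory scan the sum is 65 mm and the new lesion is still 20 mm. Nothing has worsened, and 65 is not above 78, so the episode resolves.
- The target decrease is (100 − 65)/100 = 35%. I assume this meets partial response; the protocol does not restate that cut-off. The category is iPR.
- At a third scan at least 4 weeks later with the same findings, none of the listed events for a new iUPD has occurred, so the iPR is confirmed.

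If the new lesion had instead grown to 22 mm (+2 mm), the result would be the same only if it had been selected as a New Lesion – Target, where the limit is 5 mm. Followed as a new non-target lesion, visible growth would give iCPD.

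**Step 3: comparison with a later episode** (illustrative sizes)

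Take a participant with an earlier reset and a new-lesion nadir of 20 mm. The new-lesion sum rises to 25 mm (25 − 20 = 5 mm), which gives iUPD. At the confirmatory scan it is still 25 mm and the target sum is below threshold. There is no further growth, so no iCPD, but the burden is 5 mm above its smallest value, so the exception keeps the response at iUPD. An unchanged 5 mm increase blocks iSD and iPR in a later episode, whereas an unchanged entire 20 mm new lesion does not in a first episode.

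**Step 4: size**

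Section 10.9 plans about 40 participants and gives a no-DLT example of 4 × 3 + 14 = 26, which reproduces. Taking all of them as the ORR denominator, one confirmed case is:

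- 1/40 = 2.5 percentage points
- 1/26 = 3.8 percentage points

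As an illustration with an assumed count and an assumed 95% level, 5/40 = 12.5% (4.2 to 26.8) becomes 4/40 = 10.0% (2.8 to 23.7) if one responder is not credited.

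**The case against.** The best defence is that the rule is deliberate. Persistence and resolution divide every unconfirmed case by one clear test. The section on later visits expressly provides for non-target progression that is still unresolved after a reset. Section 5.4.1.1.2 explains that iRECIST is used because response can follow the appearance of new lesions. The later-episode exception concerns an increased new-lesion burden, and in a first episode growth of 5 mm already gives iCPD, which is stricter.

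Much of this stands. The exception is not a ready-made rule for lesions unchanged since they first appeared, and it says nothing about non-target lesions. The rule may be intended, and whether it departs from the cited iRECIST publication cannot be judged from the documents. It does not follow that there is no conflict: Step 3 shows a smaller unchanged increase blocking resolution where a larger unchanged lesion does not. Section 5.4.1.1.2 also does not say that progression still present should count as resolved.

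A reader might go further and infer that the trial's response rate as a whole is inflated. The documents do not support that. Section 9.2.5 makes RECIST 1.1 the primary measure of tumour response, and it is untouched. iCR requires all lesions to resolve, growing lesions are caught as iCPD, and iSD is not a response. A reader might also infer that a count of pseudo-progressions would be distorted, but Section 10 plans no such count.

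**Conclusion.** The point holds for the iRECIST reading of ORR. As written, a first iUPD triggered solely by new or non-target lesions cannot persist. If those lesions remain without worsening, it becomes iSD, or iPR where the target sum has shrunk enough, and a confirmed iPR of this kind counts as a response. This sits in conflict of principle with the appendix's own treatment of later episodes.

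The effect is 2.5 points of ORR per confirmed case at 40 participants, or 3.8 at 26. It requires three things together: target shrinkage to iPR, trigger lesions that do not worsen, and a further scan at least 4 weeks on. How often they coincide is unknown. The analysis is descriptive, with no multiplicity control and no ORR threshold in Section 10, so this is a matter of endpoint definition and does not threaten the trial's primary safety objective.

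**What to change.** In Section 10, define an iRECIST responder for the ORR derivation. Do not credit iPR as an objective response while the new lesions or unequivocal non-target progression that triggered the iUPD are unchanged. Credit it only once the new-lesion burden has decreased or the non-target progression no longer meets PD. List the participants affected.

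Appendix 7 already has sums calculated for new target lesions. New lesions followed only qualitatively need a stated convention for what counts as a decrease. The cost is a short text change, which Section 10 handles by protocol amendment because the endpoint is secondary, and some programming. The iRECIST ORR may be slightly lower.

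Separately, the sponsor should reconcile Persistent iUPD and Resolution of iUPD with the later-episode exception, say whether the present first-episode rule is intended, and check the text against the iRECIST publication it cites. Table 7 ties imaging and treatment to iUPD status, so any consequence there is for the sponsor to decide. The endpoint rule above does not require changing a participant's iUPD status.

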### Management Following the Confirmatory Imaging

If repeat imaging does not confirm PD per iRECIST, as assessed by the Investigator, and the participant continues to be clinically stable, study treatment may continue and follow the regular imaging schedule. If PD is confirmed, participants will be discontinued from study treatment.

NOTE: If a participant has confirmed radiographic progression (iCPD) as defined above, but the participant is achieving a clinically meaningful benefit an exception to continue study treatment may be considered following consultation with the Sponsor. In this case, if study treatment is continued, tumor imaging should continue to be performed following the intervals as outlined in Section 2 and submitted to the central imaging vendor.

### Detection of Progression at Visits After Pseudo-Progression Resolves

After resolution of pseudo-progression (ie, achievement of iSD/iPR/iCR), iUPD is indicated by any of the following events:

- Target lesions
  - Sum of diameters reaches the PD threshold ( $\geq 20\%$  and  $\geq 5$  mm increase from nadir) either for the first time, or after resolution of previous pseudo-progression. The nadir is always the smallest sum of diameters seen during the entire trial, either before or after an instance of pseudo-progression.
- Non-target lesions
  - If non-target lesions have never shown unequivocal progression, their doing so for the first time results in iUPD.
  - If non-target lesions have shown previous unequivocal progression, and this progression has not resolved, iUPD results from any significant further growth of non-target lesions, taken as a whole.

- New lesions
  - New lesions appear for the first time
  - Additional new lesions appear
  - Previously identified new target lesions show an increase of  $\geq 5$  mm in the new lesion sum of diameters, from the nadir value of that sum
  - Previously identified non-target lesions show any significant growth

If any of the events above occur, the overall response for that visit is iUPD, and the iUPD evaluation process (see Assessment at the Confirmatory Imaging above) is repeated. Progression must be confirmed before iCPD can occur.

The decision process is identical to the iUPD confirmation process for the initial PD, with one exception: if new lesions occurred at a prior instance of iUPD, and at the confirmatory imaging the burden of new lesions has increased from its smallest value (for new target lesions, the sum of diameters is  $\geq 5$  mm increased from its nadir), then iUPD cannot resolve to iSD or iPR. It will remain iUPD until either a decrease in the new lesion burden allows resolution to iSD or iPR, or until a confirmatory factor causes iCPD.

Additional details about iRECIST are provided in the iRECIST publication [Seymour, L., et al 2017].
